2. DATA SOURCES

Data for the study will be derived from the following sources:

Aetna

- Aetna Membership – The Membership table captures monthly membership along with current status (e.g., active, terminated, deceased). Several demographic and plan sponsor fields are included.
- Aetna Medical Case Database – Medical Case summarizes clinical events by linking or associating all of the claims submitted for a member during the same treatment event. The logic defines clinical events based on contiguous claims for five places of service (Inpatient Acute, Inpatient Non-Acute, Emergency Room, Facility-based Outpatient Procedure, and Non-Facility Outpatient Procedure). This supports identifying all costs related to one of these events. Important to this study, Medical Case logic assigns all claims linked to a case to one category of service—inpatient, ER, or outpatient facility.
- Aetna Claims Database – Claims data include diagnoses (ICD9-CM v1 and 10-CM); professional encounters (CPT); diagnoses and procedures rendered during inpatient, outpatient and covered skilled facility encounters (ICD9-CMv3 and ICD10-PCS); durable medical equipment (HCPCS); administered (HCPCS) and dispensed (NDC) pharmaceuticals; presence of laboratory, pathology and imaging services; and allowable costs of healthcare services. Hospital claims also include DRGs, which will not be used in this study. Claims for services not covered under a member's healthplan benefits may occasionally appear in the data (i.e. provider or member submitted claim which was subsequently denied), but not reliably, and will bear a cost of zero. Laboratory, pathology and imaging services performed in-hospital or ER may not consistently appear in claims.
- Episode Treatment and Episode Risk Groups – The Aetna data warehouse contains member-level episodes-of-care resource use and cost information (via the Optum Episode Treatment Group® utility) and retrospective risk adjustment and prospective predictive cost modeling (via Optum's Episode Risk Groups®).¹ The ETG software aggregates all medical and pharmacy services related to care for specified acute (distinct beginning and end) and chronic (one year of treatment) conditions.
- Aetna's Care Management (Case and Disease) Programs – Aetna's case management program identifies members with projected limited-term intensive care needs, and helps to coordinate care, referral to specialists and centers of excellence (where

appropriate), and optimize use of insurance benefits. Disease management engages members with longer term (chronic) needs such as education, monitoring adherence, lifestyle/ behavioral aspects of care, and how to work with health care providers. Aetna Total View (ATV) is a web-based clinician application created as part of the Medical Management strategy at Aetna. The Case Management and Disease Management programs are administered in the ATV system. Survey, Assessment, and DGA (deficit goal activity) data are also available.

- Aetna Informatics Health Profile Database (HPD) – HPD identifies members with any of 84+ chronic diseases or medical conditions, the algorithms for which are comprised of medical and pharmacy claims data, and clinical laboratory data from physician claims and encounters, specialist claims, pharmacy, facilities, laboratories and others.
- Aetna Internal/External Pharmacy Data – Pharmacy data are available for all pharmacy retail and mail order claim adjudication.

Scripps Translational Science Institute

- Study Enrollment Database- This database records all interactions with study subjects enrolled in the randomized controlled trial of immediate monitoring vs. delayed monitoring, including enrollment date and randomized group status (performed by Parallel 6 through the study website), activation dates and serial numbers of all Zio patches sent to each individual subject, reasons for and dates of withdrawal from the study (including non-response after 3 attempts to contact), adverse event types and dates, participation in the Amiigo substudy, and notes on all other communications with study subjects.
- Zio Usage and Rhythm Flags-Data provided from iRhythm captured from all study Zio patch devices including patient study number and device serial number, recording start date/time, total wear time, total analyzable time, summary data for heart rate (maximum, minimum, mean), as well as data on specific arrhythmia events flagged for assessment by the study PI, including start date/time, total duration, heart rate during episode (maximum, minimum, mean).
- Principal Investigator Diagnosis of Flagged iRhythm Events and Adjudication—This database, maintained by the Principal Investigator of results of flagged rhythms received from iRhythm, records, number of unique episodes of atrial fibrillation lasting >30 seconds, average heart rate during atrial fibrillation episodes, total atrial fibrillation time and percent AF burden, also includes presence of symptoms and symptom type,

whether subject sought medical attention for symptoms, and the adjudication committee decision.

3. ANALYSIS OBJECTIVES

The analysis objectives corresponding to the study objectives listed in 1. INTRODUCTION AND BACKGROUND are the following:

Primary Analysis

1. Compare incidence of newly diagnosed atrial fibrillation (as defined by ≥ 30 seconds of atrial fibrillation or flutter detected by device, or a new clinical diagnosis recorded in claims data) at the end of the 4-month monitoring period in the immediate monitoring cohort (n=1,000) with delayed monitoring cohort (control group) (n=1,000) using ICD-9/ICD-10 codes.

Secondary Analyses

1. Compare time to first event of newly diagnosed atrial fibrillation (as defined by ≥ 30 seconds of atrial fibrillation or flutter detected by device, or a new clinical diagnosis recorded in claims data) at the end of the 4-month monitoring period in the immediate monitoring cohort (n=1,000) with delayed monitoring cohort (control group) (n=1,000) using ICD-9/ICD-10 codes.
2. Compare incidence of newly diagnosed atrial fibrillation (as defined by ≥ 30 seconds of atrial fibrillation or flutter detected by device, or a new clinical diagnosis recorded in claims data) at the end of the 4-month monitoring period in the immediate monitoring cohort (intervention group) (n=1,000) with delayed monitoring cohort (control group) (n=1,000) using HPD definition.
3. Compare prevalence of atrial fibrillation in the actively monitored cohort (n=2,000) with the matched observational control cohort (n=4,000) at 12 months.
4. Compare time to event of newly diagnosed atrial fibrillation in the actively monitored cohort (n=2,000) with the matched observational control cohort (n=4,000) at 12 months.
5. Compare the rate of initiation of anticoagulation therapy in the actively monitored cohort with the matched observational control cohort at 12 months.
6. Compare the rate of initiation of other atrial fibrillation-related therapies (antiarrhythmic agents excluding beta-blockers and calcium channel blockers, cardioversions, ablation procedures or hospitalizations with a primary diagnosis of AF) in the actively monitored cohort with the matched observational control cohort at 12 months.
7. Compare utilization in actively monitored cohort with the matched observational cohort at 12 months.
8. Compare time to first event of the combined endpoint of stroke, systemic embolism, or myocardial infarction in the actively monitored cohort with the matched observational control cohort at 3 years:

- a. In the entire cohorts.
- b. In the sub-population of individuals newly diagnosed with AF during the 3-year follow-up.

9. Compare time to first event of the combined endpoint of stroke, systemic embolism, myocardial infarction or death among subjects in the Medicare population at baseline in the actively monitored cohort with the matched observational control cohort at 3 years:

- a. In the entire cohorts.
- b. In the sub-population of individuals newly diagnosed with AF during the 3-year follow-up.

10. Compare time to first event of individual components of the combined endpoint (stroke, systemic embolism, myocardial infarction) in the actively monitored cohort with the matched observational control cohort at 3 years:

- a. In the entire cohorts.
- b. In the sub-population of individuals newly diagnosed with AF during the 3-year follow-up.

11. Compare time to first event of all-cause hospitalizations in the actively monitored cohort with the matched observational control cohort at 3 years:

- a. In the entire cohorts.
- b. In the sub-population of individuals newly diagnosed with AF during the 3-year follow-up.

12. Compare total number of all-cause hospitalizations in the actively monitored cohort with the matched observational control cohort at 3 years:

- a. In the entire cohorts.
- b. In the sub-population of individuals newly diagnosed with AF during the 3-year follow-up.

Analysis of Safety Endpoints

1. Compare time to first event of hospitalization for a primary bleeding diagnosis in the actively monitored cohort with the matched observational control cohort at 3 years:
 - a. In the entire cohorts.
 - b. In the sub-population of individuals newly diagnosed with AF during the 3-year follow-up.
2. Compare incidence of the detection of non-AF, but other actionable heart rhythm issues during monitoring in the actively monitored cohort with the matched observational control cohort in the entire cohorts at 3 years.
3. Describe incidence, timing and etiology of discontinuation of active monitoring in the monitored cohort.

Exploratory Analysis

1. Evaluate the correlation between AF detected by the Amiigo wristband with the incidence of AF detected by the Zio patch in active monitoring cohort during 4 months of active monitoring.

4. ANALYSIS SETS/POPULATIONS/SUBGROUPS

Participants

The study population is derived from the Aetna Commercial Fully Insured and Medicare populations. From this population, specific characteristics associated with an increased proportion of prevalent atrial fibrillation are identified through claims data to identify a population at increased risk for undiagnosed atrial fibrillation based on International Classification of Diseases Ninth (ICD-9) and Tenth (ICD-10) revisions diagnoses in the Aetna Claims Database or Aetna Health Analytics Profile Database (HPD):

Inclusion Criteria:

- Male age > 55 years, or females age > 65 years, and
- Prior CVA, or
- Heart failure, or
- Diagnosis of both diabetes and hypertension, or
- Mitral valve disease, or
- Left ventricular hypertrophy, or
- COPD requiring home O2, or
- Sleep apnea, or
- History of pulmonary embolism, or
- History of myocardial infarction, or
- Diagnosis of obesity

Exclusion Criteria:

- Current or prior diagnosis of atrial fibrillation, atrial flutter or atrial tachycardia
- Receiving chronic anticoagulation therapy
- Hospice care
- End stage renal disease
- Diagnosis of moderate or greater dementia
- Implantable pacemaker and/or defibrillator
- History of skin allergies to adhesive patches

Eligible Aetna members will be contacted by letter, electronically or paper, with information about the study and an invitation to learn more via a study-specific web site as well as the option to discuss with a research coordinator. Once an individual agrees to participate they will be directed to an online Informed Consent Document, or if they prefer, one will be mailed to them.

A conservative estimate is that 5% of the approached population will agree to participate in the study. With an estimated >100,000 eligible participants to approach this should allow for the recruitment of a total of 2,000 individuals for randomization and allow for development of a matched observational cohort of 4,000 individuals.

It is anticipated that 10,000 invitations will be sent out to eligible Aetna members on a rolling basis every one to two weeks with invitations continuing until ~2,100 (to account for an assumed 5% drop-out in first year) individuals have agreed to participate and signed the informed consent.

Randomized Controlled Trial Population: Immediate Monitoring (Intervention Group) vs. Delayed Monitoring (Control Group)

Upon signing the informed consent document, subjects will be randomized to either the immediate monitoring group or delayed monitoring group by random number generator. The random number generator uses Ruby's pseudo-random number generator functionality (PRNG) implemented as a modified Mersenne Twister with a period of 2**19937-1. The subject's group assignment will be sent to the STSI coordinating team. Continued eligibility of all randomized subjects for the study will be confirmed upon enrollment using Aetna databases for all inclusion and exclusion criteria.

For subjects randomized to the immediate monitoring group, the first Zio patch will be sent upon confirmation of continued eligibility. The first Zio patch will be worn by subjects in the immediate monitoring group during the first two weeks of the 4-month monitoring period. A second Zio patch will be sent to subjects in the immediate monitoring group for wear during the final two weeks of the 4-month monitoring period.

A subject will be considered withdrawn from the study if they inform the STSI study coordinating center that they wish to withdraw or if they have not initiated use of the first Zio patch after 3 notifications (e-mail/phone/e-mail) from the coordinating center.

Intention-to-treat analysis for the RCT will include all participants who are enrolled in the study according to their randomly assigned group (immediate monitoring or delayed monitoring) with the RCT follow-up time for subjects in the immediate monitoring group beginning at date of enrollment and ending at 4 months following date of enrollment or the time of completion of monitoring with their final patch, whichever is longest, and for subjects in the delayed monitoring group beginning at date of enrollment and ending at 4 months following the date of enrollment.

The per protocol analysis of the RCT will include immediate monitoring participants had analyzable data from the Zio patch for at least 30 continuous minutes any time during their assigned monitoring period and all participants in the delayed monitoring group who did not withdraw from the study prior to 4 months of follow-up.

Delayed Monitoring Group

Subjects randomized to the delayed monitoring cohort for the RCT will be actively monitored following completion of the 4 month RCT follow-up period (for which they serve as unmonitored controls). Subjects in the delayed monitoring group will receive their first Zio patch 4 months following their date of enrollment. The first Zio patch will be worn during the first two weeks of the 4-month monitoring period. A second Zio patch will be sent to subjects in the delayed monitoring group for wear during the final two weeks of the 4-month monitoring period.

Matched Observational Cohort Study: Actively Monitored (Immediate and Delayed) vs. Matched Observational Controls

For the Matched Observational Cohort study, the actively monitored group will include all subjects in the RCT who were randomly assigned to either active monitoring period (immediate or delayed).

Two matched controls will be selected for each of the 2,100 actively monitored subjects in the RCT (1,050 immediate + 1,050 delayed) from 1) the pool of subjects from the original eligible cohort who continue to be eligible based on monthly database updates and did not receive an invitation to enroll. Matching will be performed using the following criteria:

- Sex (exact)
- Age (exact by year of birth)
- CHA₂DS₂ VASc score (exact score)

CHA₂DS₂ VASc scores are re-calculated for monitored subjects at time of enrollment (updating scores calculated for eligibility of original pool). CHA₂DS₂ VASc scores are re-calculated for the pools of potential matched controls following the monthly update of the Aetna claims database and immediately prior to application of the matching protocol. Actively monitored subjects and controls will be matched on these updated CHA₂DS₂ VASc scores. Exact matches are prioritized. Matching of CHA₂DS₂ VASc score \pm 1 will be the next option if 2 exact match controls are not found for a monitored subject.

Start date for determination of outcomes from Aetna databases for both monitored subjects and matched controls will be the date of enrollment of the monitored subject. End date for the analysis of prevalence of atrial fibrillation, initiation of anticoagulation and initiation of other AF-specific interventions will be 12 months from the actively monitored subject's date of enrollment (by exact month and day). End date for analysis of outcomes at 3 years will be 3 years from the actively monitored subject's date of enrollment (by exact month and day).

For the Matched Observational Cohort Study, the ITT population will be all subjects enrolled in the RCT (actively monitored group=immediate monitoring + delayed monitoring) and their matched controls. The per protocol analysis will consist of 1) all subjects in the RCT had analyzable data from Zio patch monitoring of at least 30 continuous minutes during the RCT and who did not request removal from the observational follow-up at time of withdrawal and 2) their matched controls.

Matched Observational Cohort Study: Atrial Fibrillation Sub-population

The sub-population of subjects diagnosed with atrial fibrillation for the analyses of disease endpoints and hospitalization events will consist of subjects in the actively monitored group who received a new diagnosis of atrial fibrillation during active monitoring with the Zio patch or at any time during the 3 year follow-up by claims data and subjects in the matched observational control cohort who received a new diagnosis of atrial fibrillation based on claims data during the 3 year follow-up.

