- Compare the diagnostic capability of two different methods of rhythm screening – time-limited patch ECG monitoring versus long-term wearable pulse wave monitoring through photoplethysmography – for AF detection and tolerability.

Influence on Clinical Care

- Compare the rate of initiation of anticoagulation and other AF-specific therapies at 12-months in the active monitoring cohort versus the matched observational control cohort.
- Compare the overall incremental costs of active monitoring for AF detection versus standard of care in the 3 years following the onset of monitoring.
- Identify the impact of active AF screening versus routine care on the time to first event of the following endpoints using claims data; A) among individuals diagnosed with new AF at 3 years following the initiation of screening, and B) the entire study cohort: utilizing claims data.
 - The combined endpoint of stroke/TIA, other systemic embolization, and/or myocardial infarction.
 - In the Medicare population only, in who mortality data will be available, the combined endpoint of stroke/TIA, other systemic embolization, myocardial infarction and/or death
 - The individual components of the combined endpoint.
 - All hospitalizations.
 - Hospitalizations for bleeding events.

4. Study Design

Participants

The study population will be derived from the Aetna Commercial Fully Insured and Medicare populations. From this population specific characteristics associated with an increased proportion of prevalent atrial fibrillation will be identified through claims data and utilized to identify a population at increased risk for undiagnosed atrial fibrillation.

Inclusion Criteria:

- Male or female age > 75 or
- Male age > 55, or female age > 65, and
- Prior CVA, or
- Heart failure, or
- Diagnosis of both diabetes and hypertension, or
- Mitral valve disease, or
- Left ventricular hypertrophy, or
- COPD requiring home O2, or
- Sleep apnea, or
- History of pulmonary embolism, or
- History of myocardial infarction, or
- Diagnosis of obesity

Exclusion Criteria:

- Current or prior diagnosis of atrial fibrillation, atrial flutter or atrial tachycardia
- Receiving chronic anticoagulation therapy
- Hospice care
- End stage renal disease
- Diagnosis of moderate or greater dementia
- Implantable pacemaker and/or defibrillator
- History of skin allergies to adhesive patches
- Known metastatic cancer

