- Aetna Compassionate Care Program (ACCP) participants – individuals with advanced illness and limited life expectancy

Through the use of the above inclusion and exclusion criteria, but not excluding patients with a diagnosis of atrial fibrillation or flutter, we expect to identify a population with an overall prevalence of known AF of 10-15%. Based on prior studies supporting that 30% of the total AF population is undiagnosed, then the total AF population (X) = diagnosed AF population (0.7X) + undiagnosed AF population (0.3X). Therefore with a 12% prevalence of diagnosed AF representing only 70% of the total AF population that would suggest that the true total AF population prevalence is 17%, and therefore the prevalence of undiagnosed AF would be ~5%.

[figure not shown]
Participant Recruitment

Eligible Aetna members will be contacted by letter, electronically or paper, (Appendix 1) with information about the study and an invitation to learn more via a study-specific web site as well as the option to discuss with a research coordinator. Once an individual agrees to participate they will be directed to an online Informed Consent Document, or if they prefer, one will be mailed to them.

A conservative estimate is that 5% of the approached population will agree to participate in the study. With an estimated >100,000 eligible participants to approach this should allow for the recruitment of a total of 2000 individuals for randomization and allow for development of a matched observational cohort of 4000 individuals.

It is anticipated that 10,000 invitations will be sent out to eligible Aetna members on a rolling basis every one to two weeks with invitations continuing until ~2250 (to account for an assumed 12% drop-out in first year) individuals have agreed to participate and signed the informed consent.

Study Flow

Randomized Cohort

Following informed consent individuals will be randomized to either the immediate screening arm or the delayed screening arm. All individuals randomized to immediate screening will be sent their monitoring device(s) immediately after signing their informed consent. Their 4 months of monitoring will begin the first day their monitoring device is activated. Those randomized to delayed monitoring will receive their monitoring device(s) 4 months after the date of their informed consent being signed, with their 4 months of monitoring also starting the first day their monitoring device is activated.

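### SAP Section 4 omits one entry route and two exclusions that the protocol has, and it is the only list that the SAP's eligibility check and control-pool refresh can refer to

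*SAP*

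**What the plan says.** Protocol Section 4 (Inclusion Criteria) gives two ways in. The first is age alone: "Male or female age > 75 or". The second is "Male age > 55, or female age > 65, and" at least one of ten listed conditions. Its exclusion list has nine items, among them "Known metastatic cancer" and "Aetna Compassionate Care Program (ACCP) participants – individuals with advanced illness and limited life expectancy".

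SAP Section 4 gives only the second way in. It starts at "Male age > 55 years, or females age > 65 years, and" and goes on to the same ten conditions. Its exclusion list has seven items, with neither metastatic cancer nor ACCP. The other criteria match.

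The SAP uses eligibility in two places, both in Section 4:

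- For the randomised trial: "Continued eligibility of all randomized subjects for the study will be confirmed upon enrollment using Aetna databases for all inclusion and exclusion criteria". In the immediate group the first patch goes out only after that confirmation.
- For the matched cohort, controls come from members of the original eligible cohort "who continue to be eligible based on monthly database updates and did not receive an invitation to enroll". They are matched on sex, year of birth and CHA₂DS₂-VASc score.

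**The concern.** The SAP contains one criteria list, so an analyst working from it would take that list as the one meant by the enrolment check and the monthly refresh. It describes a different population from the protocol's, in two opposite ways. It is narrower for members over 75 who have none of the ten conditions. It is wider for members with metastatic cancer or advanced illness.

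The matched cohort is the more exposed part. Its 3-year endpoints include all-cause hospitalisation, hospitalisation for bleeding and, among Medicare members, a composite that includes death. Metastatic cancer and advanced illness bear on all of these. In the randomised part, the risk is that someone is randomised to immediate monitoring, fails the check and is never sent a patch.

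**Working it through.** **1. The two lists side by side**

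| Criterion | Protocol Section 4 | SAP Section 4 |
|---|---|---|
| Over 75, no condition needed | Eligible | No such route |
| Man over 55 or woman over 65, with at least one of ten conditions | Eligible | Eligible |
| Metastatic cancer | Excluded | Not mentioned |
| ACCP member | Excluded | Not mentioned |
| Number of exclusions | 9 | 7 |

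Only people over 75 with none of the ten conditions lose eligibility under the SAP list. Those over 75 with a listed condition still enter by the second route.

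**2. What follows depends on which list is used where**

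- *Protocol list throughout.* The analysed population is the protocol's, and the SAP text is simply wrong.
- *SAP list throughout.* Members over 75 with no listed condition are never invited and never serve as controls. Metastatic cancer and ACCP are allowed on both sides. The population differs from the protocol's, but both sides follow the same rule.
- *Protocol list for invitation, SAP list for the check and the refresh.* Some randomised subjects over 75 fail the check. Members like them leave the control pool. Members of the pool who have since developed metastatic cancer or entered ACCP are not removed.

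**3. Randomised part under the third case**

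SAP Section 4 defines ITT as everyone enrolled, and SAP Section 7 as everyone randomised. Nothing in either removes a subject who fails the check. An immediate-group subject in that position stays in the denominator, but AF can be found only through claims. That would dilute the difference in detection.

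**4. Matched part**

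The score, as set out in protocol Section 4, counts heart failure, hypertension, age, diabetes, stroke, vascular disease and sex. It has no item for cancer or advanced illness, so an exact match on it leaves both free to differ. The protocol's matching also names a propensity score; the SAP's matching criteria do not.

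The age route has a similar effect. Take a woman of 78 with hypertension only. Her score is 2 (age) + 1 (sex) + 1 (hypertension) = 4, and she is eligible under the protocol. Under the SAP list, a control of the same sex, birth year and score must also carry a listed condition. It could be one that the score ignores, such as obesity or sleep apnea. Matching does not correct that.

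**5. Stated power, as background**

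With n = 1,000 per group and two-sided alpha 0.05, power = Φ{[|p1 − p2| − 1.96·√(2p̄(1 − p̄)/n)] / √[(p1(1 − p1) + p2(1 − p2))/n]}.

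- 5% v 0.5%: (0.045 − 0.01433)/0.00724 = 4.23, power 0.99999 (SAP: above 99%).
- 2% v 0.1%: (0.019 − 0.00893)/0.00454 = 2.22, power 0.987 (SAP: 98%).

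Both reproduce. The protocol ties its expected rate to its own criteria: 12%/0.7 = 17.1% total AF, and 0.3 × 17.1% = 5.1% undiagnosed. If a different case mix lowered the monitored rate (assumed values, control at 0.5%), power would be 0.99 at 3%, 0.96 at 2.5% and 0.86 at 2%. The point is therefore about who is analysed, not about the stated power.

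**The case against.** The strongest reply is that the lists differ on paper only. The enrolment check looks at continued eligibility, which can mean changes since selection, and it does not cite the SAP list by name. Controls come from the original eligible cohort. If that cohort was built on the protocol list, the only very ill controls let in are those whose status changed before matching. The SAP still excludes hospice care, end-stage renal disease and moderate or greater dementia. The enrolment targets also differ (about 2,250 with 12% drop-out in the protocol, about 2,100 with 5% in the SAP), which suggests that the SAP section follows another protocol version.

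Much of this stands. It limits the consequence, but it does not remove the contradiction or tell an analyst which list to use. A version mismatch is an inference, and it would explain the difference without resolving it.

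Three stronger readings are tempting, and the documents do not support them:

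- *Participants over 75 are dropped from the analysis.* Both ITT definitions keep them. What the failed check puts at risk is the first patch in the immediate group.
- *The comparison is tilted in favour of screening.* A control-side excess of very ill people is plausible, because participants volunteer and controls are never invited. But the SAP list omits the same exclusions on both sides, and nothing in the documents gives the frequency of these conditions in either group. The Cox models also adjust in part through comorbidity scores.
- *Baseline metastatic cancer among the SAP Section 5 covariates shows that such patients were meant to be included.* The same list has catheter ablation, the Maze procedure and resynchronisation devices, which the SAP's own exclusions should leave empty or nearly so. It looks like a generic list.

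**Conclusion.** The contradiction is certain: one of the protocol's two entry routes and two of its nine exclusions are missing from the SAP's only criteria list. Applied as written, that list gives a different control pool from the protocol's, and the SAP's matching would not repair the difference.

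The effect on results is possible but unmeasured. Confounding could reach the 3-year comparisons of all-cause hospitalisation, bleeding hospitalisation and, in Medicare members only, the composite with death. The Kaplan-Meier comparisons are unadjusted, and the bleeding rate per person-year is described without adjustment; the Cox models mitigate in part. The documents do not give the share of participants entering by age alone, or the share of controls with metastatic cancer or in ACCP, so no size can be put on it. They also cannot show which list was programmed. The stated power is not in dispute.

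**What to change.** Reconcile SAP Section 4 with protocol Section 4 so that one list governs, and record the reason for any difference that is intended. State in the SAP that this same list is applied at the index date, meaning the monitored subject's enrolment date, to each participant and each candidate control. State also that every randomised subject stays in the ITT set whatever the check shows.

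The cost is SAP wording and a change to the eligibility program. Age and metastatic cancer are already listed as Aetna variables in SAP Section 5. ACCP is an Aetna programme, so membership should be obtainable, although the SAP does not name the table. The sample size does not change.

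### The immediate arm's RCT follow-up can outlast the control arm's by an unstated, uncapped enrolment-to-activation lag, so late claims diagnoses count in one arm only (minor)

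*SAP*

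**What the plan says.** SAP section 4 (Randomized Controlled Trial Population) sets the intention-to-treat windows by arm. In the immediate arm the clock starts on the day the subject enrols, and the end is variable: "ending at 4 months following date of enrollment or the time of completion of monitoring with their final patch, whichever is longest". For controls the window is fixed: "and for subjects in the delayed monitoring group beginning at date of enrollment and ending at 4 months following the date of enrollment".

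The second patch is sent to the "immediate monitoring group for wear during the final two weeks of the 4-month monitoring period". Protocol section 4 (Study Flow, Randomized Cohort) fixes when that period starts: "Their 4 months of monitoring will begin the first day their monitoring device is activated".

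On dispatch, the protocol says immediate-arm subjects "will be sent their monitoring device(s) immediately after signing their informed consent". The SAP sends the first patch once continued eligibility has been confirmed, and treats a subject as withdrawn only if the patch is still unused after three contacts. Neither document gives an expected or maximum time from enrolment to activation.

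SAP section 7 (Analysis of Randomized Controlled Trial) describes the primary comparison as covering the opening 4 months. It then gives an intention-to-treat window ending at the later of 4 months or final-patch completion, without separating the arms. SAP section 3 lists as its first secondary analysis: "Compare time to first event of newly diagnosed atrial fibrillation", in the same two arms. Section 7 names no test for it.

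**The concern.** The primary endpoint has two limbs: AF found on the patch, and a new clinical diagnosis in claims. Controls are unmonitored during the RCT, so only the claims limb can record an event in them. The comparison of routine diagnosis is fair only if claims are searched over equal time in both arms. Under section 4 the immediate arm's search can be longer but never shorter, so any imbalance favours screening.

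The same end dates affect the first secondary analysis. All controls leave follow-up at 4 months. If the analysis is a log-rank test or Cox model, a second-patch detection after that date has no control at risk and contributes nothing to the comparison, although it counts fully in the primary proportion. Two analyses of one question would then rest on different events, and the SAP does not say so.

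**Working it through.** **The plan's own figure.** With 1,000 per arm and two-sided alpha 0.05 (SAP section 7), 5% versus 0.5% gives power of 0.99999 by normal approximation and above 0.9999 by exact enumeration of Fisher's test. The stated value is above 99%. For 2% versus 0.1% the results are 0.987 and 0.997, against a stated 98%. Both figures reproduce.

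**Window lengths.** Let L be the days from enrolment to activation, with enrolment taken as the consent date. Four months is 4 × 365.25/12 = 121.75 days.

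- Control window: day 0 to day 121.75.
- Second patch, worn on schedule: day L + 107.75 to day L + 121.75.
- Immediate window for an on-schedule completer: day 0 to day L + 121.75, an excess of L days.
- Share of the second patch after control follow-up ends: min(L, 14)/14.

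L is not in the documents, so these values are assumptions:

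| L (days) | Share of patch 2 after control end | Excess follow-up, L/121.75 |
|---|---|---|
| 0 | 0% | 0% |
| 3 | 21% | 2.5% |
| 7 | 50% | 5.7% |
| 10 | 71% | 8.2% |
| 14 | 100% | 11.5% |
| 30 | 100% | 24.6% |

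**Claims excess in the primary proportion.** The planned control rate is 0.5% per 4 months, or 5 cases per 1,000. Taken as constant, it is 0.005/4 = 0.00125 per month.

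- Lag 0.5 month: 1,000 × 0.00125 × 0.5 = 0.63 cases (0.06 percentage points; 13% of 5).
- Lag 1 month: 1.25 cases (0.13 points; 25% of 5).
- Lag 2 months: 2.5 cases (0.25 points; 50% of 5).

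The planned difference is 5% − 0.5% = 4.5 points, so even the 2-month case is 0.25/4.5 = 5.6% of it. At this background rate these are upper bounds: they give all 1,000 subjects the extra time, and they include cases a patch has already found.

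**Cost of a common cutoff.** Suppose L is at least 14 days and all AF in both arms is cut at enrolment plus 4 months. If 25%, 40% or 50% of the 5% yield came only from the second patch (assumed shares), the immediate-arm rate would be 3.75%, 3.0% or 2.5%. Power against 0.5% would be 99.9%, 99.0% or 95.8%. In the 2% versus 0.1% scenario, losing 25% or 50% of the yield gives 94.0% or 77.7% (normal approximation throughout).

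**The case against.** The strongest reply is that following the immediate arm to the end of the final patch is a deliberate, disclosed choice. The strategy under test is two patches, and cutting it at a calendar date would discard part of its yield. That stands for patch-detected AF. It does not justify the longer claims search, which measures routine diagnosis.

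It can also be said that the claims excess is trivial beside 4.5 points, and that subjects who never complete a late second patch have the same 4 months as controls. Both are correct and are why the point is minor.

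A reader might infer more than the documents support:

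- *That the immediate arm's window runs from activation.* It does not. It begins at enrolment, and only its end depends on activation, through the final patch.
- *That most or all of the second patch necessarily falls after control follow-up.* This needs a lag above 7 days, or of at least 14 days. The eligibility check, mailing and reminders make some lag likely, but its length is not given and the protocol describes prompt dispatch.
- *That the time-to-event secondary discards second-patch detections.* This assumes log-rank or Cox, which SAP section 7 describes only for the 3-year cohort analyses. If those methods are used, a comparison over common follow-up is still valid. It leaves out late detections but does not favour screening.

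Finally, section 7's wording leaves it unclear whether claims after 4 months count at all. That is a reason to settle both sections together. Adopting section 4's rule alone would not remove the imbalance.

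**Conclusion.** The imbalance is real, follows from the SAP's own rule, and can only favour screening. Its size depends on an unstated lag. On the planned background rate it is at most about 0.06 to 0.25 points for assumed lags of 0.5 to 2 months, against a planned 4.5 points. The stated power is not affected; the issue is comparability of the estimate. The effect on the time-to-event secondary is conditional on both the lag and the unnamed method. Severity: minor.

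**What to change.** Make these changes in SAP section 4, with matching wording in section 7:

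- Count claims-diagnosed AF in both arms only to 4 months after enrolment.
- Keep counting patch-detected AF in the immediate arm to the end of the scheduled second patch, labelled as the screening strategy's yield. Saying *scheduled* also prevents an extra confirmatory patch in the wristband sub-study (Protocol section 4, Monitoring Devices) from extending the window.
- Add a sensitivity analysis of the primary endpoint with all AF in both arms cut at enrolment plus 4 months.
- State that the first secondary analysis covers the common 4 months, name its method, and report how many second-patch detections fall after it.

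The alternative of ending each control's follow-up at that subject's own later activation is not recommended. It would depend on behaviour after randomisation and would need an imputed lag for those who never activate.

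The cost is SAP wording and a date rule. Activation dates are already held in the Study Enrollment Database (SAP section 2). A few immediate-arm claims cases leave the primary count, and the two limbs of the endpoint will have different end dates, which the SAP should state openly. The common-cutoff analysis may have less power if the true rates are near the SAP's lower scenario, as shown in the working.
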